2. OBJECTIVES

The primary objective of this study is to demonstrate that reduced cocaine use results in improved cardiovascular, immune and psychosocial outcomes.

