The physiological and biological cardiovascular function tests will be the primary outcome measures from the intervention and follow up period because cardiovascular insult is one of the most troubling health problems associated with COC use. As such, previously published data regarding the effects of COC use reduction on endothelin-1 levels were used to estimate the necessary sample size for this trial. In that study, reduced COC use significantly reduced endothelin-1 levels (estimated effect size [r]=0.28), approximately half of that observed after COC abstinence. Although cardiovascular measures will be our primary outcome, it is important to note that comparable effect sizes have been observed for indicators of psychosocial outcomes as a function of reduced COC use. Effect sizes observed following COC use reduction in those studies ranged from approximately 0.15 to 0.45 for statistically significant outcomes (e.g., improved ratings of "Good Functioning" after treatment, reduced alcohol use at the end of treatment). Enrolling 66 completing subjects in each group will give us 80% power (alpha=0.05) to detect effect sizes (r) as small as 0.14 when comparing

data across the three groups. This sample size will also allow us to conduct exploratory analyses and control for any relevant biological variables that might influence outcome. Dependent variables are continuous, increasing our power relative to using dichotomous variables.

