The primary outcome measure in this study will be the influence of reduced cocaine use on endothelin-1 levels. Secondary outcome measures include other cardiovascular, immune and psychosocial function. Data will be analyzed as described in the research plan. The alpha level will be set at 5%.

As noted above, wherever possible, data are collected using an automated computer system, which increases the accuracy and completeness of data collection and ensures the validity and integrity of the data. The quality of data analyses will be monitored by random inspection by the PI and/or Co-Investigators.

Safety Monitoring Plan. Potential subjects will provide information regarding their drug use history and undergo an extensive physical and psychiatric health screening to determine their eligibility and safety of their participation. Potential subjects must meet DSM-5 criteria for moderate-severe cocaine use disorder and must present with a urine sample positive for cocaine/benzoylecgonine at the time of screening. Any potential subject with poor venous access, self-disclosed compromised immune function or who has experienced an allergic reaction to candida yeast or similar products will be excluded. Methods for monitoring adverse events (AEs) will include observations by the medical and research staff, spontaneous report by the subjects and regular measures of physiological function.

All AEs occurring during the course of each study will be collected, documented and reported to the PI and physician co-investigators. The occurrence of AEs will be assessed for the duration of participation and during the follow up visits at 2 and 4 weeks following study completion. Each week a study investigator will review the AE forms from the previous week for events that were reported as new or continuing. The study investigators will follow all AEs to the point of a satisfactory resolution. Subjects may be withdrawn from the study if the medically responsible investigator (i.e., [name], in consultation with [name] if applicable) determines it is the best decision in order to protect the safety of the subject. All AEs will be assessed to determine if they meet criteria for a serious adverse event (SAE).

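### The primary outcome is defined in two incompatible ways (all cardiovascular tests, or endothelin-1 alone), with no order of precedence and no multiplicity rule

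*Combined protocol and SAP*

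**What the plan says.** **Section 7, Sample Size Justification.** The class of cardiovascular tests is primary: "The physiological and biological cardiovascular function tests will be the primary outcome measures from the intervention and follow up period". The same paragraph repeats it: "Although cardiovascular measures will be our primary outcome". Endothelin-1 appears there as the source of the planning effect: "previously published data regarding the effects of COC use reduction on endothelin-1 levels were used to estimate the necessary sample size for this trial".

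**Section 17, Data Monitoring Plan.** One biomarker is primary: "The primary outcome measure in this study will be the influence of reduced cocaine use on endothelin-1 levels". The next sentence reads: "Secondary outcome measures include other cardiovascular, immune and psychosocial function". Section 17 then refers the analysis to the research plan and gives the error level: "The alpha level will be set at 5" percent.

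**Section 7, Data Analysis.** A significance criterion of 0.05 is stated. Under Aim 1 the weekly count of benzoylecgonine (BE)-negative urine samples is the primary predictor of cardiovascular outcomes in a generalized linear mixed model (GLMM), with endothelin-1 given as an example. The models are described as intent-to-treat, using the randomised group.

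**Section 2.** The objective spans three domains: "The primary objective of this study is to demonstrate that reduced cocaine use results in improved cardiovascular, immune and psychosocial outcomes".

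No section states an order of precedence, a testing hierarchy or an adjustment for multiple outcomes.

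**The concern.** The reactive hyperemia index, the ECG intervals, the vital signs and four of the five cardiovascular biomarkers are primary in Section 7 and secondary in Section 17. The primary outcome decides what the trial may claim as confirmed. With both definitions in force, the choice between them could be made after the results are known, and either choice would have support in the protocol.

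The two definitions also carry different error rates. One outcome tested once at 0.05 needs no adjustment. A class of a dozen or so outcomes, each tested at 0.05, does need a rule if a single positive result is enough to claim success, and the plan has none.

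**Working it through.** **1. The two definitions side by side**

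| Measure | Section 7, Sample Size Justification | Section 17 |
|---|---|---|
| Endothelin-1 | primary (one of the class) | primary |
| Other four cardiovascular biomarkers | primary | secondary |
| Reactive hyperemia index | primary | secondary |
| ECG measures | primary | secondary |
| Heart rate, blood pressure | primary | secondary |

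The sections agree only on endothelin-1.

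**2. Size of the class** (Section 7, Measures, Cardiovascular Health)

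- Reactive hyperemia index: 1.
- ECG: ventricular rate, PR, QRS, QT/QTc: 4, or 5 if QT and QTc are separate.
- Resting heart rate: 1.
- Blood pressure: 1, or 2 if systolic and diastolic are separate.
- Biomarkers: 3 endothelial and 2 platelet: 5.

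The total is 1 + 4 + 1 + 1 + 5 = 12, up to 1 + 5 + 1 + 2 + 5 = 14. It is 11 if ECG ventricular rate and resting heart rate are treated as one. C-reactive protein, which Section 7 also calls a cardiovascular marker under Immune Health, is left out.

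**3. False-positive chance if the class governs**

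The plan gives no figure of its own to reproduce here. Two inputs are assumptions: any one significant result counts as success, and the test statistics are equally correlated normals with correlation ρ, each tested two-sided at 0.05 (c = 1.96). With k outcomes:

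- Independent: 1 − 0.95^k.
- Correlated: 1 − ∫ [Φ((c − √ρ·u)/√(1−ρ)) − Φ((−c − √ρ·u)/√(1−ρ))]^k φ(u) du, by numerical integration.

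| k | ρ = 0.7 | ρ = 0.5 | ρ = 0.3 | independent |
|---|---|---|---|---|
| 11 | 22.3% | 30.4% | 37.5% | 43.1% |
| 12 | 23.2% | 31.9% | 39.7% | 46.0% |
| 14 | 24.9% | 34.8% | 43.8% | 51.2% |

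Independence is an upper case, because some measures overlap. If every measure had to succeed, there would be no inflation.

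**4. False-positive chance if endothelin-1 governs**

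One test at 0.05: 5%.

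**5. What an adjusted class would cost**

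Bonferroni gives 0.05/12 = 0.0042 and 0.05/14 = 0.0036 per measure. As a simplified guide, take a two-sided correlation test at one time point, N = 3 × 66 = 198, and the planning effect r = 0.28. Power is Φ(atanh(0.28)·√195 − z), where atanh(0.28)·√195 = 4.017.

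- One test, z = 1.960: 98%.
- 12 measures, z = 2.865: 88%.
- 14 measures, z = 2.914: 87%.

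This applies to a measure whose effect equals the endothelin-1 planning value.

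**The case against.** **Section 17 refines Section 7.** This is the best reading in the plan's favour: endothelin-1 drove the sample size, so Section 17 merely names the lead measure of the class. It does not hold, because Section 17 moves the remaining cardiovascular measures to secondary status while Section 7 calls the class primary twice. Section 17's referral to the research plan for analysis does not settle it either, because the Sample Size Justification is part of the research procedures and Aim 1 cites endothelin-1 only as an example.

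**Section 17 still leaves no defined test.** A reader might infer this, but it goes too far. Read with the Data Analysis text, Section 17 supplies an outcome, a predictor (the BE-negative count) and a model. The randomised group is not left out either: the intent-to-treat sentence says it will be used. What stays open is narrower, namely which term and which time window carry the 0.05. The power statement describes comparing "data across the three groups", whereas Aim 1 names the urine count as primary predictor.

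**Repeated visits inflate the error on endothelin-1 as well.** Table 1 has five post-baseline biomarker visits, so a reader might infer five tests with any one counting. The plan does not describe that; it specifies a longitudinal mixed model.

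**The broad objective in Section 2 is a third competing definition.** It is not. An objective covering three domains can sit above a single named outcome measure.

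**The error rates are hypothetical.** This stands. They depend on a success rule and correlations that the documents do not give, and on a count made for this review. They show what is at risk and are not a property of the plan as written.

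**Conclusion.** The contradiction is established from the text alone and needs no figure: two current passages give most cardiovascular measures different status, and nothing says which governs. It must be fixed, because the same data could be called primary success or primary failure.

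The size is conditional. If the class governs and any one unadjusted result suffices, the false-positive chance for 11 to 14 outcomes is about 22% to 44% for assumed equal correlations of 0.7 to 0.3, and 43% to 51% if independent. If endothelin-1 governs with one designated test, it is 5%. The documents do not support saying that the trial's error rate is inflated to these levels, since they state no success rule. Nor do they support saying that the analysis of endothelin-1 is undefined.

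**What to change.** Reconcile the Sample Size Justification in Section 7 with Section 17 before any analysis of outcomes by group or by BE-negative count. There are two valid routes.

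1. **Endothelin-1 alone (simplest).** Amend both sentences in the Sample Size Justification to agree with Section 17. Endothelin-1, on which the trial was sized, is the single primary outcome. The other cardiovascular measures are secondary, either adjusted for multiplicity or reported without confirmatory claims.
2. **The class.** Keep the cardiovascular measures as primary, list them, state a multiplicity rule such as Holm or Bonferroni across the list, and amend Section 17.

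Under either route, add to the Data Analysis text which term of the longitudinal GLMM carries the 0.05 (the BE-negative-count coefficient or a stated randomised-group contrast) and over which time window.

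**Cost.** The change is to text only; visits and assays are unaffected. Under route 1, other cardiovascular results can no longer be claimed as primary. Under route 2, each measure is tested at a stricter level. If the BE-count coefficient is chosen, the power statement must be restated for it, because it now describes a comparison across the three groups.

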To fill this critical knowledge gap, we propose a randomized, controlled 12-week trial using incentives to reduce COC use, with an additional 24 weeks of follow up. Over 5 years, subjects will be randomly assigned to one of three groups (n=66 completers/group): 1) high value incentives for COC abstinence in which frequency of COC use is expected to be substantially reduced or eliminated, 2) low value incentives for COC abstinence in which frequency of COC use is expected to be reduced or 3) a non-contingent control group, in which frequency of COC use is expected to remain stable. Three specific aims are proposed:

First, this study seeks to demonstrate that reduced COC use improves physiological and biochemical indicators (i.e., biomarkers) of cardiovascular function. Improvements in cardiovascular function will be assessed with physiological measures of cardiovascular fitness (e.g., peripheral arterial tonomotry) and biomarkers of endothelial (e.g., endothelin-1) and platelet (e.g., soluble CD40L) function.

Second, this study seeks to demonstrate that reduced COC use improves physiological indicators and biomarkers of immune function. Improvements will be assessed with a physiological measure (i.e., delayed-type hypersensitivity) and biomarkers of immune function (e.g., tumor necrosis factor- α , microbiome indicators).

Third, this study seeks to demonstrate that reduced COC use improves psychosocial function. Psychosocial improvements will be assessed with standardized observer and self-reported measures of mental health, drug use and risky behavior, as well as validated and sensitive cognitive behavioral tasks.

Our overarching hypothesis is that individuals assigned to the active treatment conditions (i.e., those who reduce their COC use) will display health improvements compared to individuals assigned to the noncontingent control group both during and after treatment. A "dose-response" is expected whereby individuals assigned to the high value condition will display greater reductions in COC use, and consequently greater improvements, relative to the low value group. We further hypothesize that 1) individuals assigned to active treatment conditions will display improvements from baseline through treatment completion and into follow up and 2) biomarker improvements will predict physiological outcomes.

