Study Visits. Assessments will occur at the LHBP, the CSC and/or the Gill Heart Institute as described above. For each visit, subjects will be scheduled to come to the LHBP at approximately 8 AM. They will be informed in advance of the length of the visit and any restrictions (e.g., fasting) in place, depending upon which data collection activities are planned. After arrival at the LHBP, subjects will complete standard sobriety measures, provide an observed urine sample that will be tested for the presence of a range of drugs of abuse, and then complete the battery of measures scheduled for collection at the LHBP. Subjects will then be informed of the qualitative result (i.e., BE-positive or -negative) of their urine test and told how much money will be added to their payment. Next, subjects will meet with the counselor if they are scheduled for individual counseling, and will then be transported to the CSC for a blood draw and other testing, if applicable. On days in which blood will be drawn and/or DTH tests, subjects will be instructed to fast prior to their appointment. After completion of data collection, subjects will be provided with an appointment card for their next visit, paid

with a check and discharged from the LHBP. Blood samples for laboratory chemistries and biomarkers will be transported by nursing staff to the UK Central Laboratory or BAL for storage and subsequent analysis.

Study visits fall into one of three categories: *Baseline*, *Intervention* and *Post Intervention*. *Intervention* visits are subdivided based upon the measures scheduled for completion (Table 1 below). Visits will be categorized as 3 Days/Week (approximately 1 hour each), Weekly (approximately 2 hours each), 4 Week (approximately 3 hours each) and 6 Week (approximately 4 hours). Measures that are scheduled for greater frequency will also occur at the less frequent visits (e.g., each Weekly visit will also include the 3 Days/Week measures), with the exception that measures planned for every 4 weeks will not occur at the 6 Week visit. Post Intervention visits will occur at the intervals specified in the table below for 24 weeks after a subject completes the intervention.

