urine sample outcome. Subjects will earn \$60 for each Post Intervention visit. Subjects will also earn \$15 for completing a follow up visit to have their DTH response measured 48 hours after their 4, 12 and 24 Week Post visit. To increase completion rates, subjects will receive half of the visit payment (e.g., \$30 for the 6 Week visit) at the end of each study visit. The remaining half will be paid upon study completion. If a subject completes all study visits, he or she can earn approximately \$1,230 in study payments.

Data Analysis

The statistical significance criterion is $p \le 0.05$.

Aim 1: To demonstrate that reduced COC use improves physiological and biochemical indicators (i.e., biomarkers) of cardiovascular function. Time-and group-varying weekly number of BE-negative urine samples will be analyzed as the primary predictor of cardiovascular outcomes (e.g., endothelin-1 levels) using generalized linear mixed models (GLMM; Stata 14, College Station, TX). All models will be constructed using intent-to-treat analyses including non-completing subjects, whereby the group to which the participant is randomized will be utilized. GLMM are particularly well suited for analyses of longitudinal data, as they allow for multiple observations over time, correlations among observations within an individual subject, for subjects measured at different time points and for baseline covariates (e.g., sex; age; race) and covariates that change over time (e.g., alcohol use). Although GLMM allow for missing data, any missing data will first be tested to determine whether they are missing at random or missing not at random (MNAR). Any data MNAR will be subject to multiple imputation.

Aim 2: To demonstrate that reduced COC use improves physiological indicators and biomarkers of immune function. Time- and group-varying weekly number of BE-negative urine samples will be analyzed as the primary predictor of immune outcomes (e.g., IL-10 levels) using GLMM. Other details are the same as for cardiovascular outcomes.

Aim 3: To demonstrate that reduced COC use improves psychosocial function. Time-and groupvarying weekly number of BE-negative urine samples will be analyzed as the primary predictor of psychosocial outcomes (e.g., other drug use) using GLMM. Other details are the same as for cardiovascular outcomes.

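### Does 66 completers per group really give 80% power at r=0.14, when a single-visit test gives only about 41%?

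*Combined protocol and SAP*

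**What the plan says.** The plan's only power statement is in section 7, Sample Size Justification: "Enrolling 66 completing subjects in each group will give us 80% power (alpha=0.05) to detect effect sizes (r) as small as 0.14", when the three groups are compared. The same paragraph takes its planning effect, r=0.28 for endothelin-1, from an earlier study of reduced cocaine use, and cites psychosocial effects of roughly 0.15 to 0.45.

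On what is measured and when, that paragraph says: "The physiological and biological cardiovascular function tests will be the primary outcome measures from the intervention and follow up period". Section 17 narrows this: "The primary outcome measure in this study will be the influence of reduced cocaine use on endothelin-1 levels". Table 1 schedules biomarkers at baseline, weeks 6 and 12, and 4, 12 and 24 weeks after the intervention. PAT and ECG are scheduled at baseline, week 12 and the same three follow-up visits.

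On analysis, section 7 (Data Analysis, Aim 1) chooses generalized linear mixed models because "they allow for multiple observations over time, correlations among observations within an individual subject". The main predictor is the weekly count of cocaine-negative urines. Baseline covariates are allowed; the examples are sex, age and race. Section 1 expects that the active groups "will display health improvements compared to individuals assigned to the noncontingent control group both during and after treatment", and that "individuals assigned to the high value condition will display greater reductions in COC use, and consequently greater improvements, relative to the low value group".

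**The concern.** The power sentence supplies 66 per group, alpha 0.05, three groups and an effect on the r scale. A reader who puts those into the usual formula gets about half the stated power, which looks like an arithmetic error in the only justification of the trial's size. Nothing nearby explains the difference: the sentence names no test, sidedness, number of visits, within-subject correlation, baseline adjustment or definition of r.

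If 0.14 were simply wrong, the trial could be smaller than its authors believe. A null result for a modest effect might then be read as evidence of no benefit when the trial had little chance of detecting one. The lower end of the cited psychosocial range (0.15) lies close to 0.14, so the sentence appears to promise coverage of that whole range.

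**Working it through.** **Inputs.** From section 7: 66 completers per group (N = 3 × 66 = 198), alpha 0.05, r = 0.14 as the smallest detectable effect, r = 0.28 as the planning effect. From Table 1: m = 5 post-baseline biomarker values (weeks 6 and 12; 4, 12 and 24 weeks post) and m = 4 for PAT and ECG (week 12; 4, 12 and 24 weeks post). Assumed, because the documents do not say: two-sided tests, f² = r²/(1−r²), d = 2r/√(1−r²), equal correlation rho between any two visits, and a constant effect after baseline.

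**1. The plan's figure, one visit.** At r = 0.14, f² = 0.0196/0.9804 = 0.0200 and the noncentrality is λ = 198 × 0.0200 = 3.96.

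| Test at one visit | Power, r=0.14 | Power, r=0.28 | Smallest r for 80% |
|---|---|---|---|
| Three-group F (2, 195 df) | 40.6% | 96.3% | 0.217 |
| Correlation, Fisher z, N=198 | 50.3% | 98.0% | 0.198 |
| Two groups, 66 v 66 (d=0.283 and 0.583) | 36.4% | 91.4% | 0.239 |

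The stated 80% is not reproduced at one visit. Using all 300 enrolled subjects gives 57.9% (F) or 68.0% (correlation), so that does not explain it either.

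**2. What repeated measures must contribute.** The three-group F test needs λ of about 9.78 for 80% power. The required gain over one visit is 9.78/3.96 = 2.47.

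**3. Mean of the post-baseline values, adjusted for the baseline value.** λ is multiplied by 1/[(1+(m−1)rho)/m − rho²]. For example, with m = 4 and rho = 0.3 the bracket is 1.9/4 − 0.09 = 0.385, a gain of 2.60. With m = 5 and rho = 0.3 it is 2.2/5 − 0.09 = 0.35, a gain of 2.86.

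| rho (assumed) | 4 values | 5 values |
|---|---|---|
| 0.3 | 82.0% | 85.7% |
| 0.5 | 83.1% | 85.7% |
| 0.7 | 92.2% | 93.5% |
| Lowest over rho 0 to 0.95 | 81.5% (rho 0.375) | 84.7% (rho 0.4) |

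For four values the gain is never below 2.56, which exceeds 2.47. Simulation (6,000 trials per setting) agrees: 81.4% for four values at rho 0.375, and 85.5% for five values at rho 0.5.

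**4. The same mean without baseline adjustment.** λ is multiplied by m/(1+(m−1)rho). At rho 0.3, 0.5 and 0.7, power is 73%, 60% and 51% (four values) or 76%, 62% and 51% (five values). Reaching 80% needs rho of at most about 0.21 or 0.26. With only the two in-treatment biomarker visits, an unadjusted mean has at most 71%.

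**5. Group-by-time test.** Putting the same f into the usual repeated-measures formula, λ = N f² m/(1−rho), six biomarker measurements give 94% or more for any rho from 0 up. This convention attaches r to the interaction rather than to a single visit, so it answers a somewhat different question.

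The stated figure thus fails as a single-visit figure and is reachable as a repeated-measures one.

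**The case for a change.** The strongest case for a change is that a planned mixed model does not supply the missing inputs, and the answer depends on them. Without baseline adjustment and with moderate rho, power at 0.14 falls to between 51% and 76%. The covariates named in Aim 1 do not include the baseline outcome. The dose-response prediction needs a pairwise contrast, which at r=0.14 has 73% to 87% power even with baseline adjustment and four or five values. At r=0.15, the bottom of the cited psychosocial range, single-visit power is 46% (three groups), 56% (correlation) or 41% (pair). Two or three sentences would settle the matter at almost no cost.

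Part of this stands: the sentence cannot be checked from the text alone, and stating its inputs would have been better practice. It does not show the number to be wrong. The one-visit test is not the planned analysis. The unadjusted figures also use completers only, whereas Aim 1 includes non-completers by intention to treat and section 4 plans to enrol 300. The covariates are given as examples, so a baseline value is not ruled out, and including it is ordinary practice for a longitudinal outcome. Nor is Aim 1's primary test the three-group or the pairwise comparison; it is a slope on the weekly urine count, so none of these figures is exactly its power.

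Replacing 0.14 with single-visit values of about 0.20 to 0.24 would put figures for an analysis nobody plans in place of one for a longitudinal analysis, and r would still be undefined.

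**Conclusion.** No change follows. The sentence is under-documented, but no arithmetic error has been shown. As a single-visit figure, 80% at r=0.14 would be wrong (36% to 50%). As a figure for the baseline-adjusted three-group mean of the scheduled post-baseline values it is supported, at about 81% to 94% for rho 0.3 to 0.7. That support rests on assumed compound symmetry, a constant effect after baseline, the stated conversion from r, and 198 subjects contributing all visits; the documents give no rho.

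The choice of 66 per group does not depend on the point. At the effect the plan took from earlier data, r=0.28, even one visit gives 91% to 98%. Writing out the inputs would leave enrolment, visits, models and the endothelin-1 conclusion as they are. When the results come, a null finding for a smaller effect should be judged by its confidence interval, which does not depend on the power sentence.
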